#### **5.1.1. Timing of final analysis**

The final analysis will be performed after the required number of patients has been recruited and will be performed on the data set after any 'cleaning' that may be required has been completed and the database locked. There are no plans to perform an interim analysis.

#### **5.1.2. Missing data**

No imputation for missing data shall be performed. The primary outcome analysis will only be performed on those participants with 90 day follow up, however a table to data completeness shall be provided which will capture any participants who were lost to follow-up.

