### **5.5.3 Withdrawal of Study Participants**

If a participant wishes to withdraw from the study they will be removed. We will establish whether they consent to allow the use of all data collected up to the date of removal. They will not be replaced.

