If a participant allocated to the Study arm, gets an episode of palpitations or pre-syncope and is able to record an AliveCor Heart Monitor ECG during the episode, the participant will email the ECG recorded by the AliveCor app directly to the co-ordinating Edinburgh research team at a convenient time to the participant and to a secure nhs.net email address. This email includes a pdf attachment of the ECG tracing along with the participant's AliveCor app login (which will be their IPED study number - no identifiable participant data will leave the local site, only the participants email address and IPED study number will appear), time and date of recording, and ECG recording. AliveCor collects non-sensitive usage data through a third party service called Mixpanel. Participant will not be asked to send their ECGs to AliveCor directly for analysis. The AliveCor app rhythm analysis algorithm will automatically report any ECG recorded by the AliveCor app as Normal, Atrial Fibrillation or Unclassified.

The co-ordinating Edinburgh research team will review the ECG and will contact the local study team to arrange follow-up if required. If specialist follow-up of the ECG tracing is not required then the local study team will write to the participant informing them of this (Patient ECG follow-up letter normal v2.0 24082016 and Patient ECG follow-up letter abnormal v2.0 24082016) and asking them to arrange follow up with their general practitioner who will be contacted with the report (GP Follow up Letter v2.0 24082016). The participant and GP will not be contacted further should participants record other similar ECGs that similarly do not require specialist follow-up.

If the participant records a serious significant arrhythmia i.e.

- ventricular fibrillation (VF)
- ventricular tachycardia (VT) (it will be assumed that this is symptomatic given the participant has chosen to record an ECG during the episode)
- complete or 3rd degree heart block
- second degree heart block type II (it will be assumed that this is symptomatic given the participant has chosen to record an ECG during the episode)
- pause >6 seconds
- symptomatic bradycardia <40 beats per minute

during the study period, the local study team will alert the participant immediately by telephone, and refer them urgently to their local Emergency Department or cardiac electrophysiology service (as per local protocol).

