## **8 STATISTICS AND DATA ANALYSIS**

### **8.1 SAMPLE SIZE CALCULATION**

Using a symptomatic rhythm detection rate at 90 days of 25% [3] versus standard care (10%) we estimate 110 participants in each group would have 80% power to determine a 15% improvement in symptomatic rhythm detection. We will recruit an extra 10% in each arm to allow for drop out (i.e. 121 participants in each arm). Our ED sees around 500 eligible participants a year. Assuming a 50% recruitment rate we estimate we will need to recruit for 15 months.

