## ***3. Statistical methods from protocol***

Descriptive analysis of participant characteristics shall be presented split by study arm. Baseline to 90 day change in diagnostic yield between the two study arms will be analysed using two sample t-tests or non-parametric equivalent as appropriate. Log-rank tests and Kaplan-Meier curves shall be used to examine if the smartphone recorder has an effect on detecting symptomatic rhythm and cardiac arrhythmia separately up to 90 days versus standard care. Categorical variables will be compared using a  $\chi^2$  test (and  $\chi^2$  test for trend if appropriate). All participants will be analysed on an intention to treat basis.

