### **4.2.2. Follow up assessments**

Participants in both groups will be followed up at 90 days through hospital record systems (paper or electronic depending on local policy), GP records and by telephone by the local study team. Participants will also be asked to complete a standardised written questionnaire and will receive a follow-up telephone call from the local study team enquiring about symptoms and contact with medical services. Study arm participants will also be asked about satisfaction and compliance with the heart monitor.

Participants allocated to the Study arm may be contacted by telephone by the local research team shortly after randomisation in the event of them requiring further training or setting up of the device.

If a participant allocated to the Study arm gets an episode of palpitations or pre-syncope and is able to record an AliveCor Heart Monitor ECG during the episode, the participant will email the ECG recorded by the AliveCor app directly to the co-ordinating Edinburgh research team at a convenient time to the participant and to a secure nhs.net email address.

The co-ordinating Edinburgh research team will review the ECG and will contact the local study team to arrange follow-up if required. If specialist follow-up of the ECG tracing is not required then the local study team will write to the participant informing them of this and ask them to arrange follow up with their general practitioner who will be contacted with the report. The participant and GP will not be contacted further should participants record other similar ECGs that similarly do not require specialist follow-up.

If the participant records a serious significant arrhythmia during the study period, the local study team will alert the participant immediately by telephone, and refer them urgently to their local Emergency Department or cardiac electrophysiology service (as per local protocol).

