## ***5. General Considerations***

### **5.1. Overall**

For all analyses, unless otherwise specified, participants shall be analysed according to treatment received, irrespective of the treatment group they were allocated to, with the exception of AE/SAEs. An additional table will be provided on whether the participant took part in the study and if they did not then their AE/SAEs will be included as part of the control group.

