### **6.4. Secondary outcomes**

1. The baseline to 90 day change in cardiac arrhythmia detection (i.e. presence/absence) of a smart phone based event recorder compared with standard care only shall be analysed using comparison of proportions test.
2. A log-rank test and Kaplan-Meier curves shall be used to examine if the smartphone recorder has an effect on time to first detection of symptomatic rhythm up to 90 days versus standard care only.
3. A log-rank test and Kaplan-Meier curves shall be used to examine if the smartphone recorder has an effect on time to first detection of cardiac arrhythmia rhythm up to 90 days versus standard care only.

4. The number of participants treated (or planned for treatment) for cardiac arrhythmia in those using a smart phone based event recorder versus standard care only shall be analysed using a comparison of proportions test.
5. Participant satisfaction questionnaire responses shall be compared between study arms using  $\chi^2$  test(s) (and  $\chi^2$  test(s) for trend if appropriate). A similar analysis shall be performed for participant compliance questionnaire responses.
6. The number of participants recorded for each of the following shall be collated. If appropriate and numbers allow, a two-sample t-test (or non-parametric equivalent as appropriate) shall be used to compare study arms where the outcome of interest is continuous. However if the numbers are to be treated as categorical then a  $\chi^2$  test (and if appropriate,  $\chi^2$  test for trend) shall be used to compare study arms:
  - Number of ED presentations (except index visit) due to palpitations/pre-syncope.
  - Number of inpatient hospital days (over all admissions) due to palpitations/pre-syncope.
  - Number of outpatient presentations due to palpitations/pre-syncope.
  - Number of GP presentations due to palpitations/pre-syncope (via phone follow-up).
  - Number of TRAK ECGs due to palpitations/pre-syncope.

A comparison of the overall cost-effectiveness of the smart phone based event recorder and standard care shall be provided using a two-sample t-test (or non-parametric equivalent as appropriate) between study arms. The costing scope will include primary care, secondary care and community NHS costs which shall be provided separately by the CI for analysis.

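### SAP 5.1 analyses by treatment received although the plan states intention to treat, and SAP 5.1.2 adds a complete-case primary analysis with no sensitivity analysis for missing outcomes

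*SAP*

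**What the plan says.** **Grouping**
- SAP 5.1 sets the default for all analyses except adverse events: "participants shall be analysed according to treatment received, irrespective of the treatment group they were allocated to". It allows exceptions specified elsewhere and does not define receipt of treatment.
- Protocol 8.2, carried into SAP 3, says: "All participants will be analysed on an intention to treat basis".
- SAP 6.3 compares the proportion with a detected symptomatic rhythm between recorder and standard care. It does not say whether the groups are formed by allocation or by receipt.

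**Who enters the primary analysis**
- SAP 5.1.2: "The primary outcome analysis will only be performed on those participants with 90 day follow up". It rules out imputation and offers a data completeness table.
- SAP 4.2.2: "Participants in both groups will be followed up at 90 days through hospital record systems". GP records and a telephone call are listed in the same place, and Protocol 6.2 matches. Neither document says whether one source is enough.
- Protocol 6.2, for the study arm only: "the participant will email the ECG recorded by the AliveCor app directly to the co-ordinating Edinburgh research team".
- Protocol 5.5.3, on withdrawals: "We will establish whether they consent to allow the use of all data collected up to the date of removal".
- Protocol 8.1, on loss: "We will recruit an extra 10% in each arm to allow for drop out".

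**The concern.** The two statements on grouping cannot both govern the primary comparison. One forms the groups by allocation and the other explicitly sets allocation aside. Two statisticians could each follow the documents and analyse different groups. Because the trial is open label, whether a participant takes up the device may depend on symptoms, motivation or contact with services, all of which can also affect detection. Regrouping on that basis gives up the protection of randomisation.

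The missing-data rule is a smaller departure from the same principle. A participant without 90-day follow-up leaves the primary analysis, so the promise to analyse everyone is not kept when outcomes are missing, and no planned analysis shows how much that could matter. Because the qualifying source is unstated, membership of the analysis set could also be settled after the data are seen.

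**Working it through.** **Inputs.** From Protocol 8.1: detection 25% v 10% at 90 days, 80% power, 110 per arm, plus 10% for drop-out. From Protocol 5.5.1: 121 per arm. Not in the documents, so assumed: two-sided 5% significance, the number of non-users, and the number lost per arm.

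**1. The plan's own figure.** The pooled two-proportion formula gives 100 per arm without continuity correction and 113 with it. Exact Fisher power at 110 per arm is 80.4%. The stated 110 therefore reproduces, and 110 × 1.10 = 121. The sample size is not in dispute.

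**2. Allocation v treatment received.** Suppose k of 121 study-arm participants do not take up the device and detect at the control rate of 10%.
- By allocated arm, the difference is 15 × (1 − k/121). For k = 6: 15 × 115/121 = 14.3 points. For k = 12: 15 × 109/121 = 13.5 points.
- By treatment received, the non-users join the controls. The control rate stays at 10% and the remaining study group is at 25%, so the difference is 15.0 points.

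The gap is 0.7 or 1.5 points. This case has no selection. If non-users differ from other participants in their chance of detection, the treatment-received contrast also carries a bias that the documents cannot size.

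**3. Complete-case rule with loss unrelated to detection.** Ten per cent of 121 is 12.1, taken as 12, leaving 109 per arm. Planned rates give 109 × 0.25 ≈ 27 and 109 × 0.10 ≈ 11.
- 27/109 − 11/109 = 14.7 points, z = 2.86, p = 0.004.
- All randomised: 30/121 − 12/121 = 14.9 points.

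The 0.2-point gap is whole-number rounding. The expected difference is 15.0 under either.

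**4. Bounds on that rule.** All 121 per arm stay in the denominator. The low bound sets lost study-arm participants to not detected and lost controls to detected. The high bound does the reverse.

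| Lost per arm (assumed) | Complete case | Low bound | High bound |
|---|---|---|---|
| 3 | 30/118 v 12/118 | (30 − 15)/121 = 12.4, p = 0.013 | (33 − 12)/121 = 17.4 |
| 6 | 29/115 v 12/115 | (29 − 18)/121 = 9.1, p = 0.074 | (35 − 12)/121 = 19.0 |
| 12 | 27/109 v 11/109 | (27 − 23)/121 = 3.3, p = 0.53 | (39 − 11)/121 = 23.1 |

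With 12 lost, setting every missing outcome to not detected gives 27/121 v 11/121 = 13.2 points, p = 0.005.

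Tipping point with 12 lost and no detections among the lost study-arm participants:
- 4 lost controls detected: 27/121 v 15/121, p = 0.042.
- 5 lost controls detected: 27/121 v 16/121, p = 0.064.

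**5. Why inclusion must not depend on a detection.** Suppose participants with a rhythm on file were kept and other lost participants dropped. If the 3 expected detections among the 12 lost study-arm participants had been emailed, and the 1 among lost controls was unseen, the comparison would be 30/112 v 11/109 = 16.7 points, against 14.9 for all randomised. That favours the device.

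**The case against.** On grouping, SAP 5.1 yields to anything specified elsewhere, and SAP 3 states intention to treat. But SAP 3 sits under a heading that reports the protocol's methods, and SAP 6.3 specifies nothing for the primary outcome. The exception does not clearly remove the conflict. It does cover SAP 6.2, which presents baseline data by allocated arm, so that section is not a further contradiction.

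A reader might infer that non-users would certainly be moved to the control group. The documents do not support that. Treatment received is undefined; Protocol 6.2 gives every study-arm participant the device and training, so receipt could mean being handed it. Protocol 4.3 also excludes people unwilling or unable to use it. Regrouping is possible, and its extent is unknown.

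On missing data, a reader might infer that SAP 5.1.2 discards rhythms already emailed to the research team. That needs a reading in which only day-90 contact counts, which is the less natural one. Protocol 3 and 6.2 and SAP 2 and 4.2.2 make hospital and GP records part of 90-day follow-up. An emailed ECG is reviewed centrally and either leads to follow-up or is reported to the GP, so it should normally reach those records. If a records check counts, few participants need be excluded. It is also fair that the SAP states its approach to missing data. What stands is that the qualifying source is not named and that no analysis tests the exclusion.

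**Conclusion.** The contradiction between SAP 5.1 and the intention-to-treat statement is a plain error in the documents and is the main point. Its numerical effect is unknown. Under the assumed 6 or 12 non-users detecting at the control rate, it is 0.7 or 1.5 points in favour of the device.

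The missing-data point is secondary. Loss unrelated to detection changes little. Only informative loss produces large shifts: with 12 lost per arm the limits are 3.3 to 23.1 points, and significance goes if 5 of the 12 lost controls had detections and none of the lost study-arm participants did. These are extremes under an assumed loss, not predictions. The documents show neither the size nor the direction of any bias, so they do not support a claim that the planned analysis is biased towards the device.

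**What to change.** 1. Amend SAP 5.1 so that the primary and secondary efficacy analyses are by allocated arm, in line with Protocol 8.2. Treatment received should be at most a sensitivity analysis, with receipt defined.
2. In SAP 5.1.2, state that a completed hospital or GP records check to day 90, or participant contact, counts as 90-day follow-up. Apply this identically in both arms and without regard to whether a rhythm was detected. Do not admit participants because a detection is on file. For withdrawals, follow the consent given under Protocol 5.5.3.
3. Report the number missing by arm. Add an all-randomised sensitivity analysis with missing set to not detected, plus best- and worst-case bounds. State whether a rhythm on file for someone without follow-up counts there: in the 12-lost example, counting the 3 emailed rhythms gives 30/121 v 11/121 = 15.7 points, against 13.2 if they are not counted.

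The cost is SAP wording and one extra table from data already collected. Grouping by allocation costs some power if devices go unused: at 110 per arm, pooled-test power is 83.8% with no non-use, 80.5% with 5% and 76.8% with 10%, again assuming that non-users detect at the control rate. The changes should be made before outcome data are examined.

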## **6. Final analysis**

### **6.1. Recruitment and data completeness**

Standard accrual plot and plot of number of participants recruited each quarter. Recruitment date shall be date of consent into the study.

A table presenting the completeness of participant data shall also be provided.

### **6.2. Baseline demographic statistics**

The following participant details shall be presented split by allocated study arm. Where data are continuous the mean, standard deviation, median, interquartile (IQ) range and range shall be presented and where data are binary or categorical the frequency and percentage shall be presented:

- Participant demographics
- History of presenting episode
- Past medical history
- Examination
- Admission ECG
- Management

### **6.3. Primary outcome**

The baseline to 90 day change in diagnostic yield (i.e. presence/absence symptomatic rhythm detection) of a smart phone based event recorder compared with standard care only shall be analysed using a comparison of proportions test.

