## **5.5 RANDOMISATION**

### **5.5.1 Randomisation Procedures**

Participants will be equally distributed between the two study arms with 121 participants in each arm. Randomisation will be by block randomisation. Randomisation codes will be generated and blinded envelopes will be prepared and labelled in accordance with the randomisation list for each participating site. Randomisation codes will be held by each recruiting ED in an area of the ED accessible to the research team. Participants eligible for inclusion should be randomised by taking the next lowest consecutively numbered envelope.

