## ***4. Study methods***

### **4.1. Randomisation and treatment allocation**

Participants will be equally distributed between the two study arms. Randomisation will be by block randomisation by site. An equal number of sealed opaque envelopes containing either 'Standard Care plus Device' or 'Standard Care' cards will be prepared by a central administrator not involved in the study. These will then be randomly labelled with site-specific study participation numbers and sent to each local study team. Participants eligible for inclusion will be randomised by the local study team by taking the next lowest consecutively numbered sealed opaque envelope. There will be no stratification or minimization factors.

Participants will be allocated either to (a) STUDY arm; standard care plus the use of a smart phone based event recorder or (b) CONTROL arm; standard care, depending on the group allocated in the study envelope.

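### Randomisation is blocked by site, but the primary test and both log-rank tests leave site out: valid in that respect, and mildly conservative if detection differs between sites

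*SAP*

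**What the plan says.** On allocation, SAP 4.1 states: "Randomisation will be by block randomisation by site". The envelopes are "randomly labelled with site-specific study participation numbers and sent to each local study team". Protocol 5.5.1 agrees: the envelopes are "labelled in accordance with the randomisation list for each participating site". SAP 4.1 then adds: "There will be no stratification or minimization factors".

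On analysis, SAP 6.3 says that the recorder "compared with standard care only shall be analysed using a comparison of proportions test". SAP 6.4 items 2 and 3 plan log-rank tests of the "effect on time to first detection of symptomatic rhythm up to 90 days versus standard care only" and of the "effect on time to first detection of cardiac arrhythmia rhythm up to 90 days versus standard care only". None of these names site as a stratum or covariate. The summaries of methods in Protocol 8.2 and SAP section 3 do not mention site either, and no reason is given for leaving it out.

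The trial is multi-centre, but the documents do not give the number of sites, their sizes or the block size.

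**The concern.** Separate blocked lists for each site are stratification by site, whatever the plan calls them. Blocking keeps the arms nearly balanced within each site, so differences between sites largely drop out of the true variance of the treatment difference. A pooled test still counts those differences as noise. Its standard error is then too large, the test runs below its nominal level, the confidence interval is a little too wide and some power is lost.

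Site differences are plausible here. Admission, referral and discharge follow local hospital practice in both arms (Protocol 6.2), and standard-care detection depends on that practice. The documents do not say that detection does differ by site, or by how much.

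At stake are a small amount of efficiency and a correct description of the randomisation. The validity of the primary result is not in question on this point.

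**Working it through.** **Inputs from the documents.** Detection of 25% against 10% at 90 days, 110 per arm for 80% power, 121 per arm after a 10% allowance, and 1:1 allocation (Protocol 8.1 and 5.5.1).

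**Assumptions, not in the documents.** Two-sided 5% level; 220 participants analysed; the site layouts, block schemes and site spreads given below.

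**The plan's own figure.** Without continuity correction, n per arm = [1.960 × √(2 × 0.175 × 0.825) + 0.842 × √(0.25 × 0.75 + 0.10 × 0.90)]² / 0.15² = 99.5, so 100. With continuity correction it is 113. Fisher's exact test at 110 per arm has 80.4% power, the closest match. The allowance is 110 × 1.1 = 121. The stated size is reproduced, and the present point does not affect it.

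**Analytic check of the mechanism.** With exact balance within sites and no treatment effect, the ratio of true to assumed variance is 1 − V/[p(1 − p)], where V is the between-site variance of the detection rate and p its mean. The real level of the pooled test is 2 × [1 − Φ(1.960/√ratio)]. With p = 10%, so p(1 − p) = 0.09:

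| Site rates | V | Ratio | Analytic level | Simulated pooled | Simulated stratified |
|---|---|---|---|---|---|
| Ten sites, evenly spread 5-15% | 0.00102 | 0.989 | 4.9% | 4.9-5.1% | 4.9-5.0% |
| Ten sites, evenly spread 2-18% | 0.00261 | 0.971 | 4.7% | 4.7-4.8% | 4.8% |
| Two sites, 3% and 17% | 0.00490 | 0.946 | 4.4% | 4.7% | 5.0-5.1% |
| Ten sites, half 1%, half 19% | 0.00810 | 0.910 | 4.0% | 4.1-4.3% | 4.7-5.1% |

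The simulations used blocks of 4 or one balanced block per site, with 40,000 trials each. With identical sites the pooled test ran at 5.2-5.4%, which reflects sampling and discreteness. Under simple randomisation it stayed at 5.0-5.1% in every scenario, so the conservatism comes from the blocking.

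**Main simulation, primary test.** Site effects were normal on the log-odds scale, around 25% and 10% (17.5% in both arms under the null). There were four layouts of 220: ten sites of 22; five of 44; one of 130 plus nine of 10; and sizes graded from 80 down to 4. The dominant-site layout is there because Protocol 8.1 bases recruitment on one department: "Our ED sees around 500 eligible participants a year". The pooled two-proportion z test was compared with Cochran-Mantel-Haenszel (CMH) without continuity correction, with 200,000 trials per scenario. The second block scheme makes each site's whole envelope supply one block, with a third left unused.

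| Site SD | CMH minus pooled power, blocks of 4 (points) | Same, one block per site (points) |
|---|---|---|
| 0 | -0.1 to -0.5 | -0.4 to -0.8 |
| 0.5 | +0.1 to +0.5 | -0.1 to +0.4 |
| 0.8 | +1.1 to +1.8 | +0.9 to +1.6 |
| 1.0 | +2.1 to +3.1 | +2.0 to +3.0 |

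- Type I error: pooled 4.7-4.9% at SD 0.5 and 3.8-4.4% at SD 1.0; CMH 4.9-5.1%.
- Power at SD 1.0: pooled 79.6-81.4%, CMH 81.5-84.5%.
- 95% interval for the risk difference at SD 1.0, blocks of 4: unadjusted coverage 95.8-96.0% and width 20.3-20.8 points; Mantel-Haenszel coverage 94.9% and width 19.5-19.7 points.
- Mean error of either risk difference: at most 0.04 points.

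**Log-rank tests.** Exponential times with the same 90-day probabilities, censored at day 90; three layouts, blocks of 4, 20,000 trials per scenario. Stratified minus pooled power was -0.2 to -0.4 points at SD 0, +0.3 to +0.4 at SD 0.5 and +1.8 to +2.8 at SD 1.0. Pooled type I error at SD 1.0 was 3.8-4.1%.

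**The case against.** The strongest reply is that nothing is wrong with the inference. An unadjusted comparison of proportions and an unstratified log-rank test are legitimate and err on the cautious side. The harm depends on a site spread that the documents do not report. Gains above 2 points need an SD near 1.0, which puts 95% of sites between about 1.5% and 44% detection under standard care. An SD of 0.5 already spans about 4% to 23%, and there the choice hardly matters. This stands, and it is why the point is minor.

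Four narrower objections also have substance:

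- At SD 1.0 the average rates become about 28.6% and 13.4%, so the absolute powers quoted there are not power for the planned 25% against 10%. The comparison between tests within that scenario still holds.
- The arrhythmia endpoint has no stated rate and may be rarer. A binary stand-in at an assumed 12% against 3% gave -0.6 to -0.7 points at SD 0, -0.1 to -0.3 at SD 0.5 and +1.0 to +1.4 at SD 1.0. For that endpoint the gain is smaller and appears only with a wide spread; the loss is still under one point.
- Some sites may be very small. CMH and Mantel-Haenszel methods cope with sparse strata: layouts with sites of 10 and of 4 are in the ranges above.
- The sentence on stratification may be meant as no factors beyond site. If so, it should say so.

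**Conclusion.** The point holds and is minor. SAP 4.1 describes a site-stratified randomisation and then denies any stratification, and the three tests do not use site. As far as the omission of site goes, the pooled tests are valid: unbiased, with no type I inflation. Analysis by treatment received (SAP 5.1) and restriction to those with 90-day follow-up (SAP 5.1.2) are separate matters and are not judged here.

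The size depends on an unknown spread. For the primary test it runs from a loss of up to 0.5 points of power from stratifying (0.8 with one block per site) when sites are alike, to a gain of about 2 to 3 points when they differ sharply. These figures assume 220 analysed, a two-sided 5% level and the layouts above. Confidence in the practical benefit is moderate; confidence that the text needs correcting is higher, because that does not depend on the spread.

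**What to change.** In the SAP:

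- Section 6.3: use a Cochran-Mantel-Haenszel test stratified by site, and report a Mantel-Haenszel risk difference with its 95% confidence interval.
- Section 6.4 items 2 and 3: stratify both log-rank tests by site.
- Keep the unadjusted tests as sensitivity analyses.
- Section 4.1: say that there are no stratification factors other than site.
- For completeness, state whether the other proportion tests (section 6.4 items 1, 4 and 7) are also stratified, and whether very small sites are to be combined, by a rule fixed in advance.

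The cost is wording. Site is already carried by the site-specific participant number, so no new data are needed and no values will be missing. The price in power is at most about 0.5 to 0.8 points if sites turn out not to differ.
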